7.8.2 Laboratory data

The analyses of laboratory data will be descriptive in nature and will be based on BI standards (6). If possible, analyses will be based on normalized values. If multiple reference ranges apply for one parameter (e.g. due to different age groups), analyses will be based on normalised values, which means transforming to a standard unit and a standard reference range.

Laboratory data will be analysed both quantitatively as well as qualitatively. The latter will be done by comparing laboratory data to their reference ranges. Values outside the reference range as well as values defined as clinically relevant will be highlighted in the listings.

Treatment groups will be compared based on descriptive statistics of laboratory values over time and by analysing differences from baseline. Additionally, frequency tables of changes between baseline and last values on treatment with respect to the reference ranges as well as frequencies and percentages of subjects with abnormal values or clinically relevant abnormal values will be presented.

Clinically relevant findings in laboratory data will be reported as AEs and will be analysed as part of AE analysis.

7.8.3 Vital signs

The analyses of vital signs will be descriptive in nature. Descriptive statistics of vital signs over time and for the changes from baseline (see Section 6.7) will be provided.

Clinically relevant findings in vital signs data will be reported as AEs and will be analysed as part of AE analysis.

7.8.4 ECG

Abnormal findings in the 12-lead ECG will be reported as baseline conditions (at screening) or as AEs (during the trial) if judged clinically relevant by the investigator.

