3.3.4 Removal of subject from therapy or assessments

3.3.4.1 Removal of individual subjects

An excessive withdrawal rate can have a severe negative impact on the scientific value of the trial. Every effort should be made to keep subjects in the trial as scheduled. This includes careful subject selection and appropriate explanation of the trial requirements and procedures prior to enrolment as well as an explanation of the consequences of premature withdrawal.

An individual subject is to be withdrawn from trial treatment if:

a	FEV₁ falls ≥ 45% post methacholine challenge from post diluent value If the subject is symptomatic requiring SABA the study physician must be informed and the appropriate assessments taken, regardless of time-point. The PI should be informed of the situation as soon as possible and a decision will then be made by the PI as to whether the subject is to continue to receive MCh challenges at any further visits or be withdrawn.
b	The subject has a confirmed increase in serum potassium of ≥ 5.5 mmol/L in non-haemolysed blood.

Proprietary confidential information © 2017 Boehringer Ingelheim International GmbH or one or more of its affiliated companies

c	The subject shows relevant individual QT prolongation, i.e. a QTcF increase of greater 60 ms from baseline (pre-dose Day 1 of each Treatment Period)) in connection with absolute QT or QTcF greater than 500 ms, which has been confirmed by a repeat ECG recording.
d	The subject has an asthma exacerbation.
e	The subject withdraws consent for trial treatment or trial participation, without the need to justify the decision.
f	The subject needs to take concomitant drugs that interfere with the investigational product or other trial medication
g	The subject can no longer be treated with trial medication for other medical reasons (such as surgery, adverse events, other diseases, or pregnancy)
h	The subject has repeatedly shown to be non-compliant with important trial procedures and, in the opinion of both, the investigator and sponsor representative, is not willing or able to comply with the trial requirements in the future.

If the subject agrees, he/she will undergo the procedures for early treatment discontinuation and follow up as outlined in the [Flow Chart](#) (FC) and [Section 6.2.3](#).

For all subject the reason for withdrawal (e.g. adverse events) must be recorded in the CRF. These data will be included in the trial database and reported.

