7.3.5 Safety analyses

Safety will be assessed for the further safety parameters of interest listed in [Section 5.1.3](#) based on the TS. Safety analyses will be descriptive in nature and will be based on BI standards.

Treatments will be compared in a descriptive way. The active treatment groups will be compared to the placebo group in a descriptive way. Tabulations of frequencies/proportions will be used for the evaluation of categorical (qualitative) data, and tabulations of descriptive statistics will be used to analyse continuous (quantitative) data.

The analyses will be done by ‘treatment at onset’.

Measurements (such as ECG, vital signs, or laboratory parameters) or Aes will be assigned to treatments (see [Section 4.1](#)) based on the actual treatment at the planned time of the measurement or on the recorded time of AE onset (concept of treatment emergent Aes).

Therefore, measurements planned or Aes recorded prior to first intake of trial medication will be assigned to ‘screening’, those between first trial medication intake until next intake or end of REP will be assigned to the preceding treatment, and all Aes occurring between the end of REP and next treatment intake or trial termination date respectively will be assigned to ‘follow-up’. In case of two or more treatments, the follow-up will be summarized according to the previous treatment. These assignments including the corresponding time intervals will be defined in detail in the TSAP. Please note that Aes occurring after the last per protocol contact but entered before database lock will be reported to drug safety only and will not be captured in the trial database.

Additionally, further treatment intervals (analysing treatments) may be defined in order to provide summary statistics for time intervals, such as combined treatments, on-treatment totals or periods without treatment effects (such as screening and follow-up intervals).

Adverse events will be coded using the Medical Dictionary for Regulatory Activities (MedDRA). Frequency, intensity and causal relationship of Aes will be tabulated by treatment, primary system organ class and preferred term. SAEs, AESIs ([see Section 5.3.6](#)) and other significant Aes (according to ICH E3) will be listed separately.

Laboratory data will be compared to their reference ranges. Values outside the reference range will be flagged. Additionally, differences from baseline will be evaluated.

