Vital signs, physical examinations, or other safety-relevant data observed at screening, baseline, during the course of the trial and at the end-of-trial evaluation will be assessed with regard to possible changes compared to findings before start of treatment.

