4. CHANGES IN THE PLANNED ANALYSIS OF THE STUDY

Descriptive statistics for primary and secondary endpoints will be based on the MCS rather than TS to be consistent with the model-based analyses.

There are no further changes in the planned analysis of the study.

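### SAP 7.8.4 plans no quantitative ECG summary by treatment, so QTcF shifts short of the protocol's joint withdrawal criterion would not be compared with placebo

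*SAP*

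**What the plan says.** SAP 7.8.4 is a single sentence: "Abnormal findings in the 12-lead ECG will be reported as baseline conditions (at screening) or as AEs (during the trial) if judged clinically relevant", the judgement being the investigator's. It mentions no interval values, changes from baseline or counts over a limit, and it points to no other section.

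The two preceding SAP sections go further. On laboratory data, 7.8.2 states: "Laboratory data will be analysed both quantitatively as well as qualitatively". On vital signs, 7.8.3 states: "Descriptive statistics of vital signs over time and for the changes from baseline (see Section 6.7) will be provided". Both also keep AE reporting.

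Protocol 7.3.5 sets the general rule for safety data: "tabulations of descriptive statistics will be used to analyse continuous (quantitative) data", and "The active treatment groups will be compared to the placebo group in a descriptive way". It names ECG, with vital signs and laboratory parameters, among the measurements allocated to treatments, and SAP 6.1 repeats this. It adds that, along with vital signs and physical examinations, "other safety-relevant data observed at screening, baseline, during the course of the trial and at the end-of-trial evaluation will be assessed" for change against the pre-treatment findings.

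The protocol also acts on QTcF. Withdrawal criterion c (3.3.4.1) requires "a QTcF increase of greater 60 ms from baseline", with baseline taken pre-dose on Day 1 of each period, together with an absolute QT or QTcF above 500 ms, confirmed by a repeat recording. Reason 6 for stopping the trial (3.3.4.2) applies the same joint condition to at least 2 subjects on active drug.

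SAP 4 declares one change, concerning the analysis set for descriptive statistics of the primary and secondary endpoints. It then says: "There are no further changes in the planned analysis of the study".

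**The concern.** The trial's primary objective is safety and tolerability, and the protocol synopsis lists the 12-lead ECG as a safety criterion in its own right, next to AEs. QTcF is a continuous safety variable measured repeatedly under three doses and placebo in the same subjects. A descriptive comparison by treatment is therefore what the general rule in Protocol 7.3.5 would lead a reader to expect. Under SAP 7.8.4 an on-treatment ECG reaches a table only if an investigator calls it clinically relevant.

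What is at stake is a modest dose-related shift in QTcF, or a scatter of individual increases that each stop short of the withdrawal criterion. Neither would be visible by treatment in the planned output.

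**Working it through.** The plan gives no figure to reproduce. The check is a comparison of texts, followed by a count and one step of arithmetic on the limits.

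**1. Handling by data type in the SAP**

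| Data | AE reporting | Summary over time | Change from baseline | Omission stated |
|---|---|---|---|---|
| Laboratory (7.8.2) | yes | yes | yes | – |
| Vital signs (7.8.3) | yes | yes | yes | – |
| ECG (7.8.4) | yes | none | none | no |
| Physical examination (7.8.5.1) | yes | none | none | yes |

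For physical examination the SAP says outright that no separate listing or analysis will be made. For ECG it says nothing either way. SAP 6.1 assigns ECG measurements to treatments, but no planned ECG summary uses that assignment.

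**2. Volume of data (protocol flow chart)**

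ECGs per period: Day 1 pre-dose, 1:00 and 11:30, then 23:00, 25:00 and 33:00, which makes 6 (1 before and 5 after the first dose).

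- Per subject: 6 × 4 periods = 24.
- In 36 completers (4 in Part 1, 32 in Part 2): 24 × 36 = 864.
- After the first dose: 5 × 4 × 36 = 720, of which 5 × 4 × 32 = 640 are in Part 2.
- Pre-dose: 4 × 36 = 144.

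Screening and end-of-trial ECGs are not counted.

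**3. What the joint criterion leaves out**

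Criterion c needs both a QTcF increase above 60 ms and an absolute QT or QTcF above 500 ms.

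- 500 − 60 = 440. A subject whose pre-dose QTcF is below 440 ms can rise by more than 60 ms with QTcF still at or below 500 ms. If uncorrected QT is also at or below 500 ms, criterion c is not met.
- Exclusion criterion 13 allows entry at a QTcF of up to 450 ms in men and 470 ms in women. From those values, 500 ms is passed after a rise of just over 500 − 450 = 50 ms or 500 − 470 = 30 ms. Neither need exceed 60 ms, so criterion c is again not met.

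Such subjects appear in a table only if the investigator judges the finding clinically relevant. A mean shift well under 60 ms appears in none.

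**The case against.** The strongest reply is that the SAP follows the protocol's own ECG section. Protocol 5.3.4 sends screening findings to the medical history page and clinically relevant later changes to the AE page, and SAP 7.8.4 mirrors that. This stands: AE reporting is not a departure. The gap is the absence of anything beyond it.

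A reader might infer that the SAP deleted a QTcF table the protocol had promised. The documents do not support that. The sentence on continuous data in Protocol 7.3.5 is general, ECG is named there only in the rule on assigning measurements to treatments, and no published protocol text names QTcF as a tabulated variable. The fair statement is that the SAP sits poorly with a general rule and does not say so.

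A reader might also infer that subjects crossing the stopping limits would go unseen. That is not supported either. Protocol 3.3.4.1 requires every withdrawal reason to be recorded and reported. Protocol 3.3.4.2 has the investigator and sponsor review each QT prolongation. Protocol 7.3 and SAP 7 have individual data listed. These provisions cover single cases, but a listing sorted by sequence, subject and visit is not a comparison by treatment.

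Two further points limit the concern. Protocol 5.1.3, which 7.3.5 cites as the list of further safety parameters, and SAP 7.6 are not in the published text, so an ECG summary there cannot be excluded. SAP 7.8.4 does not refer to one, however, whereas 7.8.5.2 does refer to 7.6.1 for spirometry. The prior signal is also weak. Protocol 1.2.6 reports no clinically relevant ECG abnormalities after single doses up to 3600 µg, and 2.3 names electrolyte change as the only potential systemic toxicity. That lowers the urgency. Even so, the protocol keeps QT-related exclusions, a withdrawal criterion and a trial-stopping threshold.

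**Conclusion.** The point holds as a gap in the SAP. Followed as written, the plan yields no comparison of QTcF by treatment, and SAP 4 neither declares nor justifies this. The gap covers 720 ECGs after first dose in 36 completers, 640 of them in Part 2. It concerns QTcF shifts below the joint, repeat-confirmed criterion, not cases that meet it.

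This rests on three things: the reading of the flow chart as 6 ECGs per period, full completion by 36 subjects, and the absence of an ECG summary from the two unpublished sections. The documents give no QTcF variability, so no statement is made about the size of shift the trial could show. The recommendation does not depend on one, because the summary sought is descriptive.

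**What to change.** Add to SAP 7.8.4, on the treated set:

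- Descriptive statistics of QTcF by treatment and time point, as value and as change from that period's pre-dose Day 1 value. This is the baseline in criterion c and agrees with SAP 6.7.
- Counts of subjects by treatment with (i) a QTcF increase above 60 ms, (ii) QT or QTcF above 500 ms, and (iii) the protocol's joint criterion confirmed by repeat ECG. Label (i) and (ii) as descriptive categories. They are not stopping limits on their own, and no withdrawal or stopping rule changes.

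Keep the AE reporting. A separate heart-rate table is not needed, because pulse rate is already summarised with the vital signs. If the sponsor prefers not to add the summary, SAP 4 should declare and justify the omission.

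The analysis cost is two tables. The larger cost may be the data: QT and QTcF must already be read to apply criterion c, but the published text does not say that the intervals are held in the database. If they are not, the values from 24 scheduled ECGs per subject must be entered or transferred.

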7.8.5 Others

7.8.5.1 Physical examination

Physical examination findings will be reported as relevant medical history/baseline condition (i.e., a condition already existent before intake of study drug) or as AE and will be summarised as such. No separate listing or analysis of physical examination findings will be prepared.

7.8.5.2 Pulmonary function tests

Clinically relevant findings in spirometry data (FEV1 and FVC) will be reported as AEs and will be analysed as part of AE analysis.

Descriptive statistics will be provided for FEV1 and FVC obtained at the screening visit based on the TS.

Analyses of further endpoints and parameters of interest related to PFT are described in Section [7.6.1](#).

7.8.5.3 Methacholine challenge

Descriptive statistics will be provided for the methacholine concentration (PD20) obtained from the incremental challenge during screening visit based on the TS.

9. ADDITIONAL SECTIONS

9.1 STEPS IN CASE OF CONVERGENCE PROBLEMS FOR REPEATED MEASURES MODEL

In case of convergence problems one may try one (or more) of the following steps:

- 1) Set SINGULAR=1E-10 as option (for PROC MIXED: in the model statement) – This raises the threshold at which columns are declared linearly dependent (from typically 1e-12).
- 2) Set MAXITER=100 (or even higher for PROC GLIMMIX) and/or MAXFUNC=200 (for PROC GLIMMIX, these options are available within the NLOPTIONS statement) – This increases the number of convergence iterations used from a default of 50.
- 3) Use option SCORING=4 in the final run to request a Fisher scoring algorithm to be used for the first 4 iterations.
- 4) Include the additional statement in the PROC MIXED call:
PERFORMANCE NOTTHREAD;
– this removes multi-threading from the calculations.

- 5) Provide starting values for covariance parameters using a ‘parms’ statement. Perform an initial run including the statement

```
ODS OUTPUT COVPARMS=covstart;
```

followed by a final run using

```
PARMS / PARMSDATA=covstart;
```

In the special case with the note “Convergence criteria met but final hessian is not positive definite” try instead/in addition

```
PARMS / OLS;
```

to request ordinary least squares starting values.

One may also use estimates from a simpler model (e.g. using AR(1)) as starting values for the run with TYPE=UN or UNR

In case the VC covariance matrix does not work, also in conjunction with all steps from 1)-6) mentioned above, the following covariance structures will be chosen, in the pre-defined order:

- Unstructured covariance matrix (type = UN)
- Toeplitz structure with heterogeneous variances (type = TOEPH)
- Standard Toeplitz matrix (type = TOEP)
- first-order autoregressive structure (type = AR(1))

9.2.1 Details for primary analyses

The following SAS code can be used to fit the model for the primary endpoint:

```
PROC MIXED data=indata METHOD=reml ORDER=formatted;
  CLASS SUBJID ATRTSL APERIOD;
  MODEL CHG = ATRTSL APERIOD BASE baseavg / SOLUTION DDFM = KR
    OUTP=pred;
  RANDOM INTERCEPT / SUBJECT = SUBJID TYPE=VC;
  LSMEANS ATRTSL / PDIFF=control('Placebo') CL ALPHA=0.1;
RUN ;
```

The following SAS code can be used to fit the model for the secondary endpoint 'FEV₁ AUC0-tz':

```
PROC MIXED data= indata METHOD=reml ORDER=formatted ;
  CLASS SUBJID ATRTSL APERIOD;
  MODEL LNRATIO = ATRTSL APERIOD lnbase lnbaseavg / SOLUTION DDFM
    = KR OUTP=pred;
  RANDOM INTERCEPT / SUBJECT = SUBJID TYPE=VC;
  LSMEANS ATRTSL / PDIFF=control('Placebo') CL ALPHA=0.1;
RUN ;
```

The following SAS code can be used to fit the model for the secondary endpoint 'Time to recovery':

```
PROC PHREG DATA= adtte;
  CLASS ATRTSL (REF='Placebo') APERIOD;
  MODEL aval*cnsr(1) = ATRTSL APERIOD BASEAVG / TIES=BRESLOW;
  HAZARDRATIO ATRTSL / DIFF=REF CL=WALD ALPHA=0.05;
  ODS OUTPUT HAZARDRATIOS=hazard;
RUN;
```

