18	Spirometry to be performed pre-MCh challenge, post-diluent and post methacholine dose. Post-methacholine spirometry (FEV ₁ only) timepoints will be relative to the last exhalation of methacholine solution and will be scheduled as single measurements at 30 seconds and 90 seconds, followed by duplicate measurements (FEV1 and FVC) at 5,10, 20, 30,45 minutes, 1.0, 1.25, 1.5, 1.75, 2.0, 2.25, 2.5, 2.75, 3.0, 3.5, 4.0, 4.5, 5.0, 6.0, 7.0 and 8.0 hours
19	Central laboratory: Central laboratory testing (full laboratory screen) will be performed at the screening visit (Visit 1) and on completion of the study (EOT visit / Visit 6). Details of the tests required are provided in Section 5.3.3 .
20	For female subjects: Blood HCG will be performed at screening to confirm eligibility (central laboratory)
21	Electrolytes will be measured prior to start of trial procedures and prior to discharge from the clinic on conclusion of trial procedures at each of the treatment periods (Visits 2 to 5). Initial assessment will be performed by local laboratory. In addition to local testing, a sample for electrolytes will also be sent to the central laboratory.
22	If any significant laboratory test abnormalities are detected, specifically liver function tests, the subject should return to the clinic for repeat testing
23	Spirometry to be performed pre-MCh challenge, post-diluent and post-methacholine dose. Post-methacholine spirometry (FEV ₁) timepoints will be relative to the last exhalation of final methacholine solution and will be scheduled as single measurements at 30 seconds and 90 seconds, followed by duplicate measurements (FEV1 and FVC) at 5, 10, 20, 30, 45 minutes, 1.0, 1.25, 1.5, 1.75, 2.0, 2.25, 2.5, 2.75 and 3.0 hours
24	Must be completed within 30 minutes prior to drug administration
25	FEV ₁ and FVC in triplicate, unless otherwise specified
26	The cumulative times specified in the planned time column are for orientation only. Depending on the actual a.m dosing time at the given day, the procedures and observations related to that a.m dosing (such as pre a.m dose and post a.m dose measurements of the same day) have to be adapted respectively.
27	The end of treatment (EOT) visit should be scheduled no earlier than 14 days after the last dose of study medication. In the event of early discontinuation, an additional earlier visit may be scheduled at investigator discretion.

TABLE OF CONTENTS

CLINICAL TRIAL PROTOCOL.....	1
TITLE PAGE.....	1

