6.2 DETAILS OF TRIAL PROCEDURES AT SELECTED VISITS

Methacholine (MCh) challenge

The single methacholine concentration according to [Table 6.2.1](#) (column 4) will be administered at both Day -1 or Day -2 and Day 2 of each treatment period. This concentration needed to administer this dose considers the cumulative dose administered during the incremental challenge at the screening visit (see [Table 6.2.1](#)). Single FEV₁ measurements (FEV₁ only) are then made at 30 and 90 seconds, followed by duplicate FEV₁ and FVC measurements at 5, 10, 20, 30, 45 minutes, 1, 1.25, 1.5, 1.75, 2, 2.25, 2.5, 2.75 and 3 hours on Day -2 or Day -1, with additional timepoints at 3.5, 4.0, 4.5, 5.0, 6.0, 7.0 and 8.0 hours on Day 2.

Table 6.2.1: Incremental and bolus MCh challenge dosing schedule.

Dose Number	Methacholine Concentration during Incremental Challenge (mg/ml)	Cumulative Dose (mg) (rounded to 4 d.p. max)	Methacholine Concentration to be used to administer the Bolus Challenge (mg/ml) (only highest dose number administered at Visit 1)
1	0.03125	0.0014	0.03125
2	0.03125	0.0028	0.0625
3	0.0625	0.0056	0.125
4	0.125	0.0113	0.25
5	0.25	0.0225	0.5
6	0.5	0.045	1.0
7	1.0	0.09	2.0
8	2.0	0.18	4.0
9	4.0	0.36	8.0
10	8.0	0.72	16.0
11	16.0	1.44	32.0

Spirometry

Spirometry will be performed according to ATS/ERS guidelines for pulmonary function testing [[P05-12782](#)] in order to characterise the study population, to monitor individuals' safety in regard to asthma and as an exploratory assessment of drug effect. The subject must qualify by demonstrating a pre-bronchodilator clinic measured $FEV_1 \geq 70\%$ of predicted normal. FEV_1 normal predicted values will be calculated according to GLI [[R15-0845](#)] measured ≥ 8 hours after the last use of short acting bronchodilator at the screening visit (Visit 1) and treatment period 1 Day 1.

Equipment and techniques should conform to American Thoracic Society (ATS) criteria [[P05-12782](#)].

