Spirometry will be conducted with the subject in a seated position. It is preferable that the same trained individual performs the PFTs for a given subject. Unless otherwise specified in methacholine challenges, the best of three efforts will be defined as the highest FEV_1 and the highest FVC each obtained on any of three blows meeting the ATS criteria (with a maximum of eight attempts). FEV_1 , FVC, will be measured as indicated in the [Flow Chart](#) and recorded in the eCRF. The best of the three pre-dose FEV_1 measurements will be defined as trough FEV_1 . The 24-hour clock time of the first manoeuvre for each PFT time point will be recorded.

Screening and run-in period(s)

After having been informed about the trial, all subjects will give their written informed consent in accordance with GCP and local legislation prior to enrolment in the study.

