7.2 NULL AND ALTERNATIVE HYPOTHESES

Safety and tolerability of 3 different dose strengths of BI 443651 are to be determined on the basis of the investigated parameters in comparison to placebo. It is not planned to test any statistical hypotheses with regard to these variables in a confirmatory sense. Instead, they will be described in their entirety and evaluated by descriptive statistical methods.

Confidence intervals will be computed and will have to be interpreted in the perspective of the exploratory character of the study, i.e. confidence intervals are considered as interval estimates for effects.

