The secondary endpoint time to recovery of FEV₁ within 95% of post-diluent value (see [Section 5.1.2](#)) is defined as the time from maximum reduction to last time before recovery to within 95% of pre-MCh challenge during each challenge. The time obtained from the treatment challenge represents the endpoint, while the time obtained from the baseline challenge will be used for the baseline correction in the analysis.

This secondary endpoint will be investigated using descriptive statistics for both trial parts separately and combined, if applicable.

Kaplan-Meier (KM) curves will be plotted for the recovery of FEV₁ within 95% of post-diluent value by treatment irrespective of the period it is administered in, for both trial parts separately as well as combined, if applicable.

For part II of the trial, this endpoint will be analysed using a Cox proportional hazards model as given below based on the MCS. The model includes the treatment effect and an effect for subject baseline. Thereby, the subject baseline is calculated as median of all period baselines per subject. Breslow's method for handling ties will be used.

The hazard function for the ith subject is assumed to be

$$\lambda_i(t) = \lambda_0(t) \cdot \exp\{\beta_1 X_{1i} + \beta_2 X_{2i} + \beta_3 X_{3i}\},$$

where i = 1, ..., N,

$\lambda_0(t)$ is the unspecified, non-negative, baseline hazard function

- $\beta_{1,2,3}$ are the unknown regression coefficients
- X_{1i} represents the treatment group
- X_{2i} represents the subject baseline (median of period baselines)
- X_{3i} represents the period

Proprietary confidential information © 2017 Boehringer Ingelheim International GmbH or one or more of its affiliated companies

For treatment comparisons the hazard ratios of BI 443651 vs. Placebo and asymptotic 95% Wald confidence intervals will be estimated. A hazard ratio of greater than one means that BI 443651 is not inferior to placebo.

Further details will be provided in the TSAP.

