6.7 BASELINE, TIME WINDOWS AND CALCULATED VISITS

Baseline is defined as the last measurement before first study drug administration in each treatment period.

For endpoints related to methacholine challenge baseline refers to the measurement obtained from the baseline bolus MCh challenge prior to administration of trial medication within each treatment period. The post-diluent value refers to the last measurement before methacholine administration (i.e. timepoint -0:05 relative to methacholine challenge).

Measurements taken after start of administration of trial medication will be considered on-treatment values or follow-up values, based on the definition of the study analysis phases in Section [6.1](#).

Adherence to time windows will be checked at the BRPM/DBLM.

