To this end, the endpoint will be log-transformed (natural logarithm) prior to fitting the model given above. The difference between the expected means for $\log(\text{Active}) - \log(\text{Placebo})$ will be estimated by the difference in the corresponding adjusted means (Least Squares Means), and a two-sided 90% confidence interval based on the t-distribution will be computed. These quantities will then be back-transformed to the original scale to provide the point estimate and 90% CIs for each endpoint.

For the random ‘subject’ effect in the above model a Variance Components (VC) covariance structure will be used; in case of convergence problems refer to Additional Section [9.1](#).

The SAS procedure MIXED will be used involving the restricted maximum likelihood estimation and the Kenward-Roger approximation for denominator degrees of freedom. This approach is described in Kenward and Roger ([11](#)).

Programming details are provided in Section [9.2.1](#).

Time to recovery of FEV₁ to within 95% of post-diluent value

CTP: *The secondary endpoint time to recovery of FEV₁ within 95% of post-diluent value (see Section 5.1.2 of the CTP) is defined as the time from maximum reduction to last time before recovery to within 95% of pre-MCh challenge during each challenge. The time obtained from the treatment challenge represents the endpoint, while the time obtained from the baseline challenge will be used for the baseline correction in the analysis.*

Descriptive statistics of the secondary endpoint by treatment (and by trial part) will be provided.

Kaplan-Meier (KM) curves will be plotted for the recovery of FEV₁ within 95% of post-diluent value by treatment irrespective of the period it is administered in, for both trial parts separately as well as combined, if applicable.

As a main analysis the following model will be applied to the main part of the trial (part II).

Statistical model

CTP: [...] this endpoint will be analysed using a Cox proportional hazards model as given below based on the MCS. The model includes the treatment effect and an effect for subject baseline. Thereby, the subject baseline is calculated as median of all period baselines per subject. Breslow’s method for handling ties will be used.

The hazard function for the i^{th} subject is assumed to be

$$\lambda_i(t) = \lambda_0(t) \cdot \exp\{\beta_1 X_{1i} + \beta_2 X_{2i} + \beta_3 X_{3i}\},$$

where $i = 1, \dots, N$,

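### Breslow's ties method, fixed for time to recovery, pulls the hazard ratio slightly towards 1 when recovery times are tied on the reading grid; Efron's method removes most of this at almost no cost

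*SAP*

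**What the plan says.** **Ties.** SAP 9.2.1 gives the Cox model as "MODEL aval*cnsr(1) = ATRTSL APERIOD BASEAVG / TIES=BRESLOW". SAP 7.5, repeating Protocol 7.3.2, names Breslow and says that his "method for handling ties will be used". No alternative or sensitivity analysis for ties is given.

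**Endpoint.** Protocol 7.3.2 defines it as "the time from maximum reduction to last time before recovery" to within 95%. Both ends are spirometry readings.

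**Grid.** Protocol 6.2 lists the readings after methacholine for both challenges, "with additional timepoints at 3.5, 4.0, 4.5, 5.0, 6.0, 7.0 and 8.0 hours on Day 2". Guidance note 18 of the Flow Chart places them "relative to the last exhalation of methacholine solution and will be scheduled as single measurements at 30 seconds and 90 seconds", then at longer intervals.

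**Which times.** Protocol 6.2 (Spirometry) states: "The 24-hour clock time of the first manoeuvre for each PFT time point will be recorded". SAP 6.7 identifies the post-diluent reading by a nominal time, "timepoint -0:05 relative to methacholine challenge". Neither SAP 7.5 nor SAP 9.2.1 says which kind of time forms the analysis variable.

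**Use of the result.** Under Protocol 7.2 "confidence intervals are considered as interval estimates for effects". Protocol 7.3.2 reads a hazard ratio above 1 as the drug being not inferior to placebo, so a value below 1 means slower recovery.

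**The concern.** Breslow's approximation is accurate when few events share a time. Here a small set of readings has to carry some 128 recoveries, so shared times are likely unless unrounded clock times are used. The resulting error has one direction, towards a hazard ratio of 1. The trial looks for a harmful effect on the airways and reports this hazard ratio as an effect estimate. An avoidable pull towards no difference is therefore in the unwelcome direction, even if it is small.

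**Working it through.** The plan states no expected hazard ratio, number of events or number of ties for this endpoint, so there is no figure to reproduce.

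**1. Grid and records.** 30 s and 90 s (2), 5 to 45 min (5), 1 to 3 h in quarter hours (9) and 3.5 to 8 h (7) give 2 + 5 + 9 + 7 = 23 Day 2 readings; the baseline challenge has 16. Part 2 has 32 completers × 4 periods = 128 records (Protocol 7.7). If most maxima fall at one early reading, planned times took about 23 to 32 distinct values in simulation, or 128/32 = 4 to 128/23 = 5.6 records per value.

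**2. Why Breslow attenuates.** At a time with d tied recoveries, let S be the sum of exp(βx) over all subject-periods still unrecovered and D the same sum over the d that recover.
- Breslow's denominator is S^d.
- Efron's is the product over k = 0, …, d−1 of (S − (k/d)·D).

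Breslow keeps all d in the risk set for each of the d events. With d = 1 the two formulas are the same.

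**3. Size near a hazard ratio of 0.65.** Assumptions, none of them in the documents: log-normal recovery, log-SD 0.4 within and 0.4 between subjects, median 1 h, recovery 22% longer on 1200 µg only. The design is the Williams sequences of Table 3.1:2 with treatment, period and subject-median baseline in the model. The rows marked † come from a separate simulation of the same endpoint.

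| Times analysed | Breslow | Efron | Untied | Breslow − Efron |
|---|---|---|---|---|
| Planned, 80% of maxima at 90 s (2000 runs) | 0.671 | 0.645 | 0.636 | 0.026 |
| The same, repeated (3000 runs) | 0.680 | 0.654 | 0.648 | 0.026 |
| Planned, 80% of maxima at 90 s † | 0.687 | 0.661 | 0.653 | 0.026 |
| Planned, maxima 20/40/30/10% at 30 s, 90 s, 5 and 10 min (500 runs) | 0.658 | 0.645 | 0.640 | 0.013 |
| Clock times to the minute † | 0.664 | 0.655 | 0.647 | 0.009 |

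In the first row Efron closes (0.671 − 0.645)/(0.671 − 0.636) = 74% of the gap to untied times. Over five recovery models with whole-minute clock times the shift was 0.005 to 0.011.

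**4. What else the size depends on.** A second set of assumptions: Weibull recovery with shape 1.5, subject log-hazard SD 0.5, the same hazard ratio for all doses, planned times, 200 runs per setting. Loss = 1 − ln(HR Breslow)/ln(HR untied). Each range runs from all maxima at 30 s to maxima spread evenly over the first five readings.

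| Assumed HR, placebo median | Untied | Breslow | Efron | Loss of log HR, Breslow |
|---|---|---|---|---|
| 0.7, 60 min | 0.717 | 0.742 to 0.724 | 0.719 to 0.717 | 10.0% to 2.8% |
| 0.5, 30 min | 0.521 | 0.577 to 0.541 | 0.529 to 0.526 | 15.6% to 5.7% |
| 0.5, 60 min | 0.521 | 0.554 to 0.532 | 0.523 | 9.3% to 3.2% |
| 0.5, 120 min | 0.519 to 0.518 | 0.544 to 0.525 | 0.521 to 0.519 | 7.3% to 2.0% |
| 2.0, 30 min | 1.932 | 1.669 to 1.823 | 1.885 to 1.909 | 22.2% to 8.8% |

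Efron lost at most 3.7% in any setting. Clock times to the minute with Breslow still lost about 1% to 14%.

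**5. Against the uncertainty.** ln(0.671/0.645) = 0.04; with a model standard error of about 0.26 this is 0.04/0.26 = 0.15 standard errors. A 95% interval around 0.65 would be exp(ln 0.65 ± 1.96 × 0.26) = 0.39 to 1.08.

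**6. Interval width.** The measure is mean model standard error divided by the empirical SD of the estimate; 1 is ideal.
- Breslow, 80% of maxima at 90 s: 1.07 to 1.17 over five recovery models. The separate simulation († above) gave 1.00 to 1.04.
- Efron: 0.94 to 1.04 over all tied settings of step 3; 0.89 to 0.96 in the separate simulation.
- Untied times: 0.94 to 1.02 and 0.90 to 0.95 respectively.

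The code has no subject term, so within-subject correlation is ignored. That is not the whole explanation of the narrowness. In the repeated run under no treatment effect, untied times gave 0.935 with no between-subject variation at all, and 0.948 with a between-subject log-SD of 0.6.

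**The case against.** Breslow's method is a recognised approximation, specified in advance, and the same in protocol and SAP. Nothing contradicts anything. The shift is about 0.15 standard errors, no hypothesis is tested, and a pull towards 1 does not on average carry an estimate across 1. The Kaplan-Meier curves and the AUC0-tz analysis also show delayed recovery and are untouched. Clock times are collected, and if they are analysed unrounded the problem all but disappears. All of this stands, and it is why the point is minor. It does not remove the point: the error has one direction, in a trial that treats its intervals as effect estimates, and one code option removes most of it.

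It is also fair that Efron is not better in every respect. Its interval can be slightly too narrow, and Breslow's extra width partly masks this. Masking is not a correction, however, because the width comes from the ties and changes with them.

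**Conclusion.** The point holds as a minor improvement. With tied times, Breslow understates a delayed recovery by about 0.01 to 0.03 in hazard ratio at a true value near 0.65, compared with Efron on the same data; the gap to untied times is a little larger (0.034 and 0.035 in two of the heavily clustered examples). The size depends on the clustering of the maxima, the speed of recovery and the true hazard ratio, and grows with fast recovery or a strong effect. All sizes rest on assumed distributions.

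Three stronger readings are tempting and not supported:
- A reader might infer that Breslow's interval is too wide in general. The ratio of standard error to SD was close to 1 in several settings and clearly above it only in some heavily clustered ones.
- A reader might infer that planned times will be used. The nominal time in SAP 6.7 identifies a reading; it does not say how elapsed time is computed.
- A reader might infer that the silence on planned or recorded times is the main defect. It is a missing detail. Efron is the safer choice either way, since whole-minute clock times also tie.

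**What to change.** Replace TIES=BRESLOW with TIES=EFRON in SAP 9.2.1, name Efron's method in SAP 7.5, and list the departure from Protocol 7.3.2 in SAP section 4, which now reports no change other than the analysis set for the descriptive statistics. As a clarification, add a sentence to SAP 7.5 saying whether planned or recorded clock times form the event time, at both the maximum and the last reading before recovery.

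The cost is one code option and a few sentences. No new data are needed, and the results are identical if there are no ties. The price is a narrower interval that can be slightly too narrow. A subject-clustered variance or a frailty term could be added as an optional sensitivity analysis, but a frailty term changes the quantity estimated and neither was better calibrated at 32 subjects.
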